4.2 Participant Disposition

An overall summary table of the participant disposition will be prepared with number and percentages of participants in the following categories (and sub-categories):

- Screened and randomised participants
- Analysis sets (safety-, ITT-, mITT-, mITT2-, PP-, and immunogenicity analysis set)
- Cohort (safety and immunogenicity)
- End of trial status (completed, completed with recurrent TB or early termination)

- Early termination from trial including reasons, with percentage calculated using total withdrawn as denominator

The summary table will be by treatment and in total. The denominator will be the number of randomised participants and relative to randomised treatment for calculation of the percentages.

Early termination including reason will in addition be summarised by treatment and period, where period is defined as from Visit 3, Day 0 until the day before Visit 5, Day 56, from Visit 5, Day 56 until the day before Visit 7, Day 238, and from Visit 7, Day 238 until Visit 8, Day 421.

Failure to meet inclusion/exclusion criteria will be summarised by criterion overall based on all who failed to meet at least one criterion.

All disposition information will be listed. Screening failures will be listed including reason for failure. A listing of all randomised participants will be provided including randomisation number and block ID.

4.3 Baseline Characteristics and Demographics

Demographics and baseline characteristics will be presented as key characteristics:

- Age
- Age-group: 18 - 35, 36 – 60 years
- Sex
- Race
- Country

And other characteristics:

- Height
- Weight
- Body mass index (BMI)
- BMI group: 13 to <25, 25 and above kg/m²
- Smoking status
- Site

Demographics and baseline characteristics will be listed (including details of smoking history) and summarised using descriptive statistics, by treatment and in total for the ITT analysis set.

Demographics and baseline characteristics will also be summarised for the mITT analysis set in case the mITT contains less than 90% of the participants in the ITT analysis set. Similar summaries will be made for the PP analysis set in case this set contains less than 80% of the participants in the ITT analysis set.

Additional baseline characteristics deemed to be of immunologic or epidemiologic importance, have biological plausible relation to the risk of TB disease relapse or have been associated with risk of TB disease relapse in previous literature are listed below and will be grouped as indicated:

- Anemia (yes/no) defined for women as hemoglobin < 12 g/dL versus \geq 12 g/dL, and for men as hemoglobin < 13 g/dL versus \geq 13 g/dL
- Diabetes Mellitus versus no diabetes, (yes/no), defined as participants with medical history high level term *Diabetes mellitus (incl subtypes)* which includes non-insulin dependent types.
- Any comorbidity versus no comorbidity at baseline, (yes/no), please see section 4.4 for a definition.

The additional baseline characteristics will be summarised by treatment and listed by participant for the ITT analysis set.

4.4 Medical History

Relevant medical history and surgical history is collected. Medical and surgical history will be summarised by treatment, system organ class (SOC), and preferred term (PT), and listed using the ITT analysis set.

In addition, comorbidity terms defined as participants with a history of chronic or intermittent diseases, medical conditions or symptoms judged to influence the primary endpoint as assessed by the medical expert of the trial will be summarised by treatment, SOC, and PT using the ITT analysis set. The participants will be classified by the medical expert before unblinding of the trial and the classification will be documented in the DBL minutes.

5 Exposure and Other Dosing Information

5.1 Exposure

Number of vaccinations, timing of 2nd vaccination relative to first vaccination 1st, days from 2nd vaccination to end of trial, and trial duration defined as time from 1st vaccination to end of trial in days will be summarised using descriptive statistics and presented for the safety analysis set according to vaccination actually received.

All information including reason no injection was administered or not administered per protocol, date and time of injection, injection site, whether injection site was examined and whether there were any post dose adverse events (AEs) will be listed by participant and injection number.

5.2 Concomitant medication and TB treatment history

Concomitant medication at baseline and changes in concomitant medication during the trial will be recorded. All concomitant medication including new TB treatment will be summarised by ATC level 4 term and generic drug name and treatment. Concomitant medication as well as new TB treatment will be listed using the ITT analysis set.

TB diagnosis and treatment history will be recorded at the first and second screening visit. Time from TB diagnosis to screening visit 2, TB treatment, Time from 1st vaccination to TB treatment stop date, Duration of TB treatment at screening visit 2, Time from completion of 22 weeks of TB treatment to screening visit 2, and Time from completion of 22 weeks of TB treatment to 1st vaccination will be summarised and all information (date of TB diagnosis, start and completion date of treatment for current episode) will be listed for the ITT analysis set. See section 8.2 for handling of partial or missing dates.

5.2.1 Prohibited Medication

Prohibited medication during the trial comprises receipt of:

- Investigational drug or investigational vaccine from visit 1 until and including visit 8 (Day 421)
- Licensed vaccine from visit 1 until and including visit 6 (Day 70) except for SARS-Cov-2 vaccines recommended by national vaccination programs if administered more than 28 days before or after IMP.
- Treatment likely to modify the immune response (e.g., blood products, immunoglobulins, immunosuppressive treatment) from 42 days before visit 3 until and including visit 6 (Day 70). Inhaled and topical corticosteroids are permitted.

Please see appendix D for a definition.

Prohibited medication received during the trial will be listed by participant.

6 Statistical Methodology for Efficacy Endpoints

All analyses with trial site as an effect will be performed without trial site as an effect if data is too sparse.

6.1 Time-to-event analyses

Time-to-event analyses will have start- and end-timepoint depending on the endpoint and analysis set as described in Table 1 and Table 2 below:

Table 1: Start-timepoints in time-to-event analyses

Endpoints	Population	Start-timepoint (Day=0)
All	All	Excluded from analysis if withdrawal or event before the day of the start-timepoint.
Primary endpoint (TB recurrence)	PP	Date of 2 nd vaccination + 14 days
Primary endpoint (TB recurrence) Secondary endpoint (TB disease relapse) Secondary endpoint (TB disease reinfection)	mITT	1. If received 2 nd vaccination then date of 2 nd vaccination + 14 except if withdrawn before 2. If missed 2 nd vaccination and visit 6 is within ± 3 days visit window (Day 67 to 73) then visit 6 3. Else Day 70 except if withdrawn before
1 st exploratory endpoint (TB recurrence or new TB treatment) 2 nd exploratory endpoint (TB recurrence - Xpert MTB/RIF Ultra or culture of sputum)	ITT	Date of 1 st vaccination
3 rd exploratory endpoint (TB recurrence)	mITT2	Date of 1 st vaccination + 30 except if withdrawn before

If TB event is not within the period between the start-timepoint and end-timepoint, then the participant will be censored as described in Table 2. Events on the day of the start time-point are included in the analyses with a time-to-event duration of 1 day.

Table 2: End-timepoints in time-to-event analyses

Endpoint	Population	End-timepoint
All	All	Completing the trial, terminating early or lost-to-follow-up without events are censored at the day of the last visit. End-timepoint is always on the day or after the start-timepoint.
Primary endpoint (TB recurrence)	PP mITT ITT	Event: 1. Date of sputum collection for culture-confirmed TB disease Censored: Earliest date of the following: 1. Date of last visit or TC, regardless of whether two sputum samples were collected 2. Date of sputum collection resulting in positive Xpert MTB/RIF Ultra (if followed by new TB treatment) for culture negative participants 3. Date of onset of new TB treatment, in the absence of any prior culture-confirmed TB disease recurrence


TB disease relapse
	
mITT ITT
	
Event: 1. Date of sputum collection for culture-confirmed TB disease relapse Censored: Earliest date of the following: 1. Date of last visit or TC, regardless of whether two sputum samples were collected 2. Date of sputum collection resulting in confirmed TB disease reinfection 3. Date of sputum collection resulting in positive Xpert MTB/RIF Ultra (if followed by new TB treatment) for culture negative participants 4. Date of onset of new TB treatment, in the absence of any prior culture-confirmed TB recurrence

TB disease reinfection
	
mITT ITT
	
Event: 1. Date of sputum collection for culture-confirmed TB disease reinfection Censored: Earliest date of the following: 1. Date of last visit or TC, regardless of whether two sputum samples were collected at the last visit 2. Date of sputum collection resulting in confirmed TB disease relapse 3. Date of sputum collection resulting in positive Xpert MTB/RIF Ultra (if followed by new TB treatment) for culture negative participants. 4. Date of onset of new TB treatment, in the absence of any prior culture-confirmed TB recurrence

1st Exploratory TB recurrence or new TB treatment
	
mITT ITT
	
Event: Earliest date of the following: 1. Date of sputum collection for culture confirmed TB disease 2. Onset TB treatment (in the absence of any prior culture-confirmed TB disease recurrence) Censored: 1. Date of last visit or TC, regardless of whether two sputum samples were collected

2nd Exploratory TB recurrence - Xpert MTB/RIF Ultra or culture of sputum
	
mITT ITT
	
Event: Earliest date of the following: 1. Date of sputum collection for confirmed TB disease recurrence 2. Date of sputum collection for Xpert MTB/RIF Ultra-confirmed TB disease recurrence Censored: Earliest date of the following: 1. Date of last visit or TC, regardless of whether two sputum samples were collected at the last visit

		2. Date of onset of TB treatment (in the absence of any prior culture- or Xpert-confirmed TB disease recurrence)
3 rd Exploratory TB recurrence	mITT2	
Event: Date of sputum collection for culture-confirmed TB disease no earlier than 30 days after 1st vaccination
 
Censored: Earliest date of the following:
 
 1. If received 2nd vaccination then date of 2nd vaccination + 14 except if withdrawn before, else if missed 2nd vaccination and visit 6 is within ±3 days visit window (Day 67 to 73) then visit 6 else Day 70 2. Date of last visit or TC, regardless of whether two sputum samples were collected 3. Date of sputum collection resulting in positive Xpert MTB/RIF Ultra (if followed by new TB treatment) for culture negative participants 4. Date of onset of new TB treatment, in the absence of any prior culture-confirmed TB disease recurrence

Time to event (or censoring) in days will be calculated as

$$\text{Date}_{\text{end-timepoint}} - \text{Date}_{\text{start-timepoint}} + 1$$

Censoring will only be used if no events are available after the start timepoint. If last visit is used as censoring and the last visit occurs later than the visit window of visit 8 then day 428 will be used as end timepoint. Participants censored later than day 428 due to other censoring events will not be transferred to day 428.

New TB treatment is defined in Appendix E.

The trial was designed for the primary endpoint to be evaluated using a one-side α -level of 10%, therefore a one-sided log-rank p-value and 80% VE profile confidence limits will be presented for the primary endpoint. Two-sided p-values and 95% VE profile confidence intervals will be presented as well.

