3.1 Major protocol deviations

Deviations from the protocol will be registered as protocol deviations with classification:

- Major
- Minor

and category

- Informed consent
- Eligibility criteria

- Withdrawal criteria not adhered to
- Dosing deviation
- Visit window
- Missed procedure(s)
- Specimen deviation
- Unblinding
- Safety reporting
- Other

Before DBL and unblinding, all protocol deviations will be evaluated. Protocol deviations classified as major can lead to exclusion from PP analysis set. The decisions will be documented in the DBL minutes.

The following will be assessed as major protocol deviations:

- Violation of inclusion criteria 5, 6 or 7
- Receipt of any investigational TB vaccine previously (excl. crit. 10)
- Receipt of any new investigational drug or investigational vaccine from Visit 1 through Visit 8 (excl. crit. 11)
- Receipt of any licensed vaccine from Visit 1 through Visit 6 (excl. crit. 12) except for SARS-Cov-2 vaccines recommended by national vaccination programs, which will be allowed if given > 28 days before and from the time of administration of clinical trial product.
- Receipt of treatment likely to modify the immune response (e.g., blood products, immunoglobulins, immunosuppressive treatment) within 42 days before Visit 3 through Visit 6. Inhaled and topical corticosteroids are permitted (excl. crit. 13)
- Received TB treatment (Rifampicin, Isoniazid, Pyrazinamide or Ethambutol) for current episode for more than 28 weeks
- Received the second vaccine outside visit window. The window was extended to two months after day 56 during the Covid-19 pandemic.
- Did not receive the 2nd vaccination
- Did not receive treatment as randomised
- HIV+ detection between Visit 3, Day 0 and Visit 6, Day 70 (14 days after the 2nd vaccination)
- Other protocol deviations which are assessed as having a clinically or statistically significant effect

Protocol deviations leading to exclusion from the PP analysis set will be summarised by treatment and in total. Number and percentages of participants will be presented, and percentages will be based on all randomised participants. Covid-19 related protocol deviations will be summarised by treatment, classification, (major/minor), and category. A similar summary of all protocol deviations will be made. Protocol deviations are rated into major or minor in the eCRF.

All protocol deviations will be listed by participant.

4 Planned Statistical Methods

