6.5 Analysis and presentation of exploratory efficacy endpoints

Three exploratory efficacy endpoints linked to the primary endpoint are defined as follows:

1. Rate of TB recurrence, defined as participants meeting the primary endpoint of TB recurrence or who started TB treatment without confirmation of *Mtb* by culture of sputum
2. Rate of TB recurrence, defined as participants meeting the primary endpoint of TB disease recurrence based on confirmation of *Mtb* by Xpert MTB/RIF Ultra or culture of sputum
3. Rate of TB recurrence, defined as participants meeting the primary endpoint of TB disease recurrence or diagnosed between 30 days after the 1st vaccination and 14 days after the 2nd vaccination, based on confirmation of *Mtb* by culture of sputum

The analysis set for the 1st and 2nd exploratory endpoint (1. and 2. above) will be the mITT set and these analyses will be repeated using the ITT analysis set. The 3rd exploratory endpoint (3. above) will be analysed using the mITT2 set. See section 3 for definition of analysis sets.

The following analyses will be performed for the three exploratory endpoints: Time to TB disease recurrence will be estimated using the KM method and presented by treatment in a cumulative plot (inverted KM estimates) with 95% confidence bands, median time to TB, and the p-value from a two-sided log-rank test.

The endpoints will additionally be analysed using a Cox proportional hazard regression model, including treatment and site as categorical effects. Treatment group inference will be evaluated using a two-sided likelihood ratio test. Vaccine efficacy (VE) will be calculated as 1 minus the hazard ratio for H56:IC31 versus placebo and presented together with both 80% and 95% profile confidence limits.

The incidence of TB disease recurrence per 100 person-years of follow-up and associated 95% confidence limits will be presented by treatment. The relative risk between H56:IC31 and placebo with 95% confidence limits will be presented as well.

The Cox proportional hazard analysis will be repeated including country instead of site as categorical effect.

Details will be listed by trial site and participant.

6.5.1 1st exploratory endpoint: Rate of TB disease recurrence (relapse or reinfection)

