1st exploratory Endpoint, Rate of TB disease recurrence (relapse or reinfection), is defined as participants meeting the primary endpoint of TB disease recurrence or who started TB treatment without confirmation of *Mtb* by culture of sputum.

The number (and percentage) of participants meeting the 1st exploratory endpoint will be summarised by treatment group. The summary will include the number of participants who started new TB treatment without culture confirmation of TB recurrence.

6.5.2 2nd exploratory endpoint: Rate of TB disease recurrence (relapse or reinfection)

2nd exploratory endpoint, Rate of TB disease recurrence (relapse or reinfection), is defined as participants meeting the primary endpoint of TB disease recurrence based on confirmation of *Mtb* by Xpert *MTB*/RIF Ultra or culture of sputum.

The number (and percentage) of participants meeting the 2nd exploratory endpoint will be summarised by treatment group. The summary will include the number of participants positive by Xpert *MTB*/RIF Ultra only and by Xpert *MTB*/RIF Ultra and culture.

6.5.3 3rd exploratory endpoint: Rate of TB disease recurrence (relapse or reinfection)

3rd exploratory endpoint, Rate of TB disease recurrence (relapse or reinfection), is defined as participants meeting the primary endpoint of TB disease recurrence AND participants diagnosed between 30 days after the 1st vaccination and 14 days after the 2nd vaccination, based on confirmation of *Mtb* by culture of sputum. The endpoint is similar to the primary endpoint, except that TB disease recurrence diagnosed between 30 days after the 1st dose and 14 days after the 2nd dose (or Day 70) is included as well.

The analysis set for this endpoint will be the mITT2 set.

The number (and percentage) of participants meeting the 3rd exploratory endpoint will be summarised by treatment group.

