8.3 Other derivations

Duration of AEs

Duration of an AE in days will be calculated as:

$$\text{Date}_{\text{AE end}} - \text{Date}_{\text{AE start}} + 1$$

The calculation will be based on AE dates after handling of partial dates. Duration will not be calculated for ongoing AEs.

Time to event

Time to event (or censoring) in days will be calculated as

$$\text{Date}_{\text{end-timepoint}} - \text{Date}_{\text{start-timepoint}} + 1$$

9 Deviations from protocol

The following deviations in the statistical analyses compared to the protocol are made:

- The protocol section 6.1 states that the per-protocol [PP] analysis set will consist of all participants who received both doses of H56:IC31 or placebo within the specified dose intervals, who entered the evaluation period for efficacy 14 days after receipt of the second dose of H56:IC31 or placebo with no HIV seroconversion, and who had no major protocol deviations (to be defined in the statistical analysis plan). Regarding major protocol deviations, the definition is updated to *who had no major protocol deviation of clinical or statistical significance*.
- The protocol section 7.3.1 states that supportive robustness and consistency analysis will be performed using the PP and ITT populations for the primary endpoint. Since
 - the only difference between the mITT and the ITT population is that the mITT will include all randomised participants except those with TB disease recurrence before Visit 6, Day 70
 - the primary endpoint only include TBs diagnosed by confirmation of *Mtb* by culture of sputum, during the period starting 14 days after the 2nd vaccination (Day 70, Visit 6) then are the mITT and ITT analyses exactly identical, why the ITT analyses of the primary endpoint from day 70 will be replaced by analyses from day 0.
- The protocol section 7.3.1 states that summaries of median time to initial diagnosis of TB disease recurrence will be presented by treatment group and trial site. Due to the expected low number of recurrent TB diseases, it will not be possible to estimate the median time to initial diagnosis and this is therefore not included in the SAP. The endpoint contains censored events and a non-parametric summary of time to TB disease recurrence is not appropriate.

10 Software

All statistical calculations described in this SAP will be done by using SAS, release 9.4 or later (SAS Institute, Cary, NC, USA).

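### SAP Table 2 censors event-free participants at about Day 70 for the 3rd exploratory endpoint, although its events count to Day 421, so the Kaplan-Meier, median and Cox results are wrong as written

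*SAP*

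**What the plan says.** SAP Section 6.5.3 describes the 3rd exploratory endpoint as follows: "The endpoint is similar to the primary endpoint, except that TB disease recurrence diagnosed between 30 days after the 1st dose" and the end of the post-dose-2 lead-in is counted as well. The primary endpoint closes at Day 421, so this one runs from Day 30 to Day 421. Table 1 starts it at 1st vaccination plus 30 days, and its event rule in Table 2 has no upper limit.

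The censoring cell takes the earliest of four dates. Item 1 reads: "If received 2nd vaccination then date of 2nd vaccination + 14 except if withdrawn before, else if missed 2nd vaccination", with an in-window Visit 6 or Day 70 as fallback. Items 2 to 4 are the last visit or call, a positive Xpert followed by new treatment in culture-negative participants, and the start of new TB treatment.

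Three other statements in Section 6.1 bear on this:
- The general row of Table 2: "Completing the trial, terminating early or lost-to-follow-up without events are censored at the day of the last visit".
- Below Table 2: "Censoring will only be used if no events are available after the start timepoint".
- Between the two tables: "If TB event is not within the period between the start-timepoint and end-timepoint, then the participant will be censored".

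For this endpoint Section 6.5 plans a "cumulative plot (inverted KM estimates) with 95% confidence bands, median time to TB, and the p-value from a two-sided log-rank test", and a Cox model giving vaccine efficacy (VE) with 80% and 95% limits.

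**The concern.** Item 1 is the date on which the primary endpoint's follow-up begins. Its wording is nearly that of the mITT start rule in Table 1, and no other endpoint in Table 2 has such an item. That it was carried over by mistake is an inference; that it conflicts with Section 6.5.3 and with the general row is not.

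If later events are kept, whether a person stays at risk after about Day 70 depends on whether that person will later have the event. Kaplan-Meier and Cox both require censoring that does not depend on the future outcome. A programmer who follows Table 2 literally would report a curve rising to 100% recurrence, an artificial median time to TB, and a VE near zero even if the vaccine worked as assumed. For the primary endpoint, SAP Section 9 itself says of the median: "Due to the expected low number of recurrent TB diseases, it will not be possible to estimate the median time to initial diagnosis".

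**Working it through.** **Inputs.** SAP Section 2.2.1: 450 per arm, 4% per year on placebo, VE 60%, 10% dropout, two-sided alpha 20%. SAP Section 6.1: start at Day 30, item 1 at Day 70 for an on-time second dose. End of endpoint: Day 421.

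**The plan's own figure.** Expected events: 450 × 0.90 × (0.04 + 0.04 × 0.40) = 22.68, i.e. the stated 23. Required events (Schoenfeld): 4 × (1.2816 + 0.8416)² / (ln 0.4)² = 21.5, so 22; 23 events give 82% power. The sample size is reproduced, and item 1 plays no part in it.

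**Risk time.** Event-free participants contribute 70 − 30 = 40 days to an endpoint that spans 421 − 30 = 391 days.

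**What correct censoring should show.** 391 / 365.25 = 1.07 years. Cumulative incidence is 1 − exp(−0.04 × 1.07) = 4.2% on placebo and 1 − exp(−0.016 × 1.07) = 1.7% on vaccine (1.6% in the simulation). The median is never reached. About 25 events are expected with dropout: about 2.8 in Days 30 to 70 and about 22.3 later.

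**As written, later events kept.** The 22.3 later cases split 1 : 0.4, about 15.9 placebo and 6.4 vaccine. After Day 70 these are the only people at risk, and all of them have the event.
- At the last event in each arm one person is at risk, so the survival estimate is multiplied by 1 − 1/1 = 0 and the inverted curve ends at 100%.
- Each arm's share of the later events equals its share of the risk set, so those events point to a hazard ratio near 1. Only the 2.8 early events carry the true contrast.

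**Simulation.** 5,000 trials per scenario; constant hazard unless stated, dropout uniform over Days 30 to 421, no site effect, unstratified two-sided log-rank, Cox with treatment only. The p < 0.05 threshold is illustrative, because the SAP sets none for this endpoint.

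| Scenario | Median VE, as written | Median VE, item 1 deleted | p < 0.05, as written | p < 0.05, item 1 deleted |
|---|---|---|---|---|
| VE 60%, all second doses on time | 11% | 60% | 6% | 58% |
| VE 60%, 10% / 20% / 30% of second doses late | 21% / 23% / 24% | – | 7–8% | – |
| VE 60%, front-loaded hazard (Weibull shape 0.6, same 12-month risk) | 26% | 60% | 9% | 58% |
| No effect | – | – | 5.7% | 5.0% |

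The late-dose rows reflect SAP Section 3.1: "The window was extended to two months after day 56 during the Covid-19 pandemic". That puts item 1 as late as about 56 + 60 + 14 = Day 130; the runs spread it uniformly over Days 80 to 130. The late shares are assumed.

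In the on-time scenario the curve ends at 100% in both arms, and a median is computable in both arms in over 99% of trials (typically 205 days placebo and 196 days vaccine from the Day 30 start).

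A second simulation (800 trials per scenario, exponential dropout) gives a median VE of 12% as written against 60% at 4% per year. Over the 2% to 8% recurrence range in Protocol Section 1.1, the as-written VE is 7% to 14%.

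**Other reading: events after the item 1 date are ignored.** About 2.8 of about 25 events remain, or 6.6 of 25 if the hazard is front-loaded. The analysis would be internally valid but would cover only about Days 30 to 70. That contradicts Section 6.5.3 and table shell 14.2.9.1, whose layout runs to end of trial.

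**The case against.** The strongest reply is that little depends on this row. The endpoint is exploratory, with no success criterion and no multiplicity control. The primary, relapse and reinfection rows do not contain item 1. Section 9 adds an ITT analysis of culture-confirmed recurrence from Day 0 under the primary censoring list, so a near-duplicate, correctly censored result is already planned. Table 14.2.9.1 will still give correct case counts. All of this stands, and it limits the consequence to the mITT2 time-to-event results.

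Second, the 11% figure comes from the most extreme case, every second dose on time, which fits poorly with the Covid-extended window. That is fair: 21% to 24% is the better guide if some doses were late. It is still far from 60%.

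Third, the climb to 100% occurs only if later events override item 1. That is also true, but the other reading discards most of the events the endpoint is defined to include.

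Fourth, p < 0.05 is not the plan's threshold. At the design's two-sided 20% level, simulated rejection rates are 22% as written against 83% corrected, so the conclusion does not change.

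**Conclusion.** The row is wrong on either reading, and no other part of the SAP repairs it. If later events are kept, the Kaplan-Meier curve and median are artefacts, and a true VE of 60% is estimated at about 11% with on-time dosing and 21% to 26% in the late-dose and front-loaded scenarios. The log-rank test loses most of its power, but its size under no effect is roughly kept, so the error does not create false positives. If later events are dropped, roughly nine in ten expected events are lost under a constant hazard.

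The sizes rest on the plan's design assumptions plus the assumed dropout pattern, hazard shape and late-dose shares; the contradiction itself rests on none of them.

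Case counts and percentages are unaffected. The effect on incidence per 100 person-years is undetermined. Section 6.5 defines no person-time for this endpoint, and the Section 6.2 formula starts 14 days after dose 2, so it cannot be used unchanged from Day 30. If Table 2 end dates were used, placebo person-years would fall from about 448 to 56, and the placebo rate would rise from about 4.0 to about 32 per 100.

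**What to change.** In SAP Table 2, 3rd exploratory endpoint, delete item 1 of the censoring list and keep items 2 to 4. The row then matches the primary endpoint's list: the earliest of last visit or call, Xpert-positive sputum followed by new TB treatment in culture-negative participants, and onset of new TB treatment without prior culture confirmation. In Section 6.5, state that person-time for this endpoint runs from the Table 1 start date (1st vaccination plus 30 days) to the corrected Table 2 end date.

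The cost is one deleted line and one added sentence in the SAP, plus the matching derivation for Tables 14.2.9.2 and 14.2.9.3, the Kaplan-Meier plot and, for person-time, Table 14.2.9.4. No new data are needed and no other endpoint changes. It should be done before unblinding, because a later correction would alter a prespecified rule with the results in view; if that point has passed, the change should be reported as an SAP deviation in the clinical trial report.
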